5.1 Inclusion Criteria

Participants are eligible to be included in the study only if all the following criteria apply:

Category	Criterion
Age	1. Are 18 to 68 (inclusive) years of age at the time of signing the informed consent.
Type of Participant and Disease Characteristics	2. Are overtly healthy as determined by medical evaluation, including no clinically significant abnormality identified on physical examination or laboratory evaluation and no active clinically significant disorder, condition, infection or disease that would pose a risk to participant safety or interfere with the study evaluation, procedures, or completion.
Weight	3. Have a body weight within 50.0 and 100.0 kg (inclusive) and body mass index within the range 19.0 and 30.0 kg/m ² (inclusive).
Sex and Contraception/Barrier Requirements	4. Female participants who are not a WOCBP See Appendix 3 for definitions.
Informed Consent	5. Capable of giving signed informed consent, as indicated in Appendix 2 , which includes compliance with the requirements and restrictions listed in the ICF and this protocol.
Smoking	6. Are nonsmokers for at least 6 months preceding Screening.

5.2 Exclusion Criteria

Participants are excluded from the study if any of the following criteria apply:

Category	Criterion
Medical Conditions	
 History or presence of clinically relevant respiratory, gastrointestinal, renal, hepatic, hematological, lymphatic, neurological, cardiovascular, psychiatric, musculoskeletal, genitourinary, immunological, dermatological, connective tissue diseases or disorders, as determined by medical evaluation. Individuals with diagnosis of hemochromatosis, Wilson's disease, alpha 1 antitrypsin deficiency, or any other chronic liver disease including Gilbert's disease will be excluded from the study. Prior history of splenectomy or any clinically relevant surgery within 3 months prior to Screening.

Category	Criterion
	
4. History of any malignancy.5. History of chronic or recurrent acute infection or any bacterial, viral, parasitic or fungal infections within 30 days prior to Screening and at any time between Screening and admission, or hospitalization due to infection within 6 months prior to Screening.6. History of shingles within 12 months prior to Screening.7. History of drug hypersensitivity, ascertained or presumptive allergy/hypersensitivity to the active drug substance and/or formulation ingredients; history of serious allergic reactions leading to hospitalization or any other hypersensitivity reaction in general, which may affect the safety of the participant and/or outcome of the study per the Investigator's discretion.8. History of alcoholism or drug abuse within 2 years prior to Screening, or positive for drugs of abuse or alcohol by the laboratory assays conducted during Screening and Day -1.9. History of residential exposure to tuberculosis, or a positive QuantiFERON® test within 4 weeks prior to or at the time of Screening.10. Administration of live vaccines or live-attenuated virus vaccines within 3 months prior to Screening. Administration of other types of vaccines (e.g., SARS-CoV-2 vaccines) is allowed until 4 weeks before admission to CRU, thereafter it is prohibited until the end of the study. Note: In case of clinical symptoms, the participant should be symptom-free for at least 1 week prior to admission to CRU.11. Any condition, including findings in the laboratory tests, medical history, or other Screening assessments, that in the opinion of the Investigator constitutes an inappropriate risk or a contraindication for participation in the study or that could interfere with the study's objectives, conduct, or evaluation.
Prior/Concomitant Therapy	12. Weak, moderate or strong inhibitors or inducers of CYP3A4/5 (table of substrates, inhibitors, and inducers) within 4 weeks prior to the first administration of study intervention.

Category	Criterion
	
13. Use of any prescribed medicine or over-the-counter drug or dietary supplement, including herbal remedies, vitamins, and minerals, antacids and dietary supplements such as fish oils within 2 weeks or 5 times the half-life of the respective drug, whichever is longer, prior to the first administration of study intervention.
 
Occasional ibuprofen up to 1200 mg per day is permitted.

Prior/Concurrent Clinical Study Experience	
14. Use of any investigational drug in any clinical study within 60 days prior to Study Day 1 administration or have used an experimental monoclonal antibody within the past 1 year prior to Study Day 1 or have participated in a study evaluating a BTK inhibitor within 60 days, or are on extended follow-up in a clinical study, even if last administration of an IMP was more than 60 days ago, or 5 half-lives of the investigational drug, whichever is longer, prior to Screening.

Diagnostic Assessments	
15. Medical history and physical examination results that include any ongoing clinically relevant findings as judged by the Investigator.
 
16. Clinically relevant findings (excluding minor, not clinically relevant excursions from normal ranges, as judged by the Investigator) at Screening in biochemistry, hematology, coagulation, and urinalysis examinations for the age of the participant, as judged by the Investigator:
 
Alanine aminotransferase, aspartate aminotransferase: above 1.3-fold upper limit of normal Note: Levels of alanine aminotransferase and aspartate aminotransferase may increase physiologically towards early post menopause (Tiwari 2018, Petroff 2022, Matsui 2016). Therefore, inclusion of participants with slight elevations from ULN for alanine aminotransferase and aspartate aminotransferase levels can be justified for postmenopausal women.Creatinine: above 1.2-fold upper limit of normalAbsolute lymphocyte count, absolute neutrophil count: below limit of reference range

Category	Criterion
	17. Estimated glomerular filtration rate according to the Chronic Kidney Disease Epidemiology Collaboration Creatinine Equation (2009) < 75 mL/min at Screening.
	18. Semi-supine systolic blood pressure > 140 mmHg or < 90 mmHg, diastolic blood pressure > 90 mmHg or < 50 mmHg, and pulse rate > 90 or < 50 bpm at Screening. Any abnormal blood pressure results may be repeated once and if the repeat result is within the normal range, it is not considered to have met the exclusion criterion.
	19. 12-lead ECG showing a QTcF > 450 ms, PR > 215 ms, or QRS > 120 ms.
	20. 24-hour Holter ECG at screening for participants above 45 years of age showing clinically relevant abnormalities.
	21. Positive for a) hepatitis B surface antigen, hepatitis B core antibody, hepatitis C antibody, or human immunodeficiency virus I and II tests at Screening; b) SARS-CoV-2 at Screening or Day -1.
	22. Use of hormonal preparations (estrogens and/or progestin and/or androgens including anabolic steroids): 
• Short-acting hormonal preparations within 8 weeks (oral, transdermal, vaginal) before first study treatment administration until Follow-Up Visit.• Long-acting hormonal preparations within 6 months (intramuscularly/ subcutaneously administered depot preparations, implants, intra-uterine system) before first study treatment administration until Follow-Up Visit.
Other Exclusions	23. Consumption of an average weekly alcohol intake of > 7 units/week for women. One unit is equivalent to 8 g of alcohol: a half pint (~ 240 mL) of beer, 1 glass (125 mL) of wine or 1 (25 mL) measure of spirits.

Category	Criterion
	24. Excessive consumption of xanthine-containing food or beverages (> 5 cups of coffee a day or equivalent) or inability to stop consuming caffeine, from 48 hours prior to study intervention administration until after collection of the final PK sample.
	25. Consumption of alcohol from 48 hours prior to first administration of study intervention.
	26. Herbal supplements including, but not limited to, St. John's wort, grapefruit, Seville oranges, cranberries, or juices of these fruits within 14 days prior to the first administration of study intervention.
	27. Donation or loss of more than 450 mL of blood in the 60 days prior to Screening, donation of plasma from 2 weeks prior to Screening, or platelets from 6 weeks prior to Screening.
	28. Travel to a country with a high prevalence of tropical diseases within 3 months prior to Screening.
	29. Inability to communicate reliably with the Investigator or considered by the Investigator to be unable to or unlikely to co-operate with the requirements of the study.

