1.1 Synopsis

Protocol Title: A Phase I, Open-Label, Multiple-Dose Study of the Effect of Evobrutinib on the Pharmacokinetics of a Combined Oral Contraceptive in Healthy Female Participants

Short Title: Effect of Evobrutinib on Pharmacokinetics of a Combined Oral Contraceptive (COC)

Rationale: Embryo-fetal toxicity studies in female mice and rabbits indicate a teratogenic potential of evobrutinib. Thus, a study to evaluate the drug-drug interaction potential of evobrutinib on COC components is required according to FDA and EMA guidance.

The intent of this study is to assess the effect of evobrutinib on the pharmacokinetics of the COC ethinyl estradiol/norethisterone in healthy female participants. **CCI**

Objectives and Endpoints:

Objectives	Endpoints	Ref. #
Primary		
To investigate the effect of multiple doses of evobrutinib on EE/NET PK in healthy participants	Plasma EE/NET: AUC _{0-∞} C _{max}	1
Secondary		
To assess the safety and tolerability of evobrutinib when administered together with EE/NET in healthy participants	Nature, occurrence, and severity of TEAEs Absolute values and changes in safety laboratory tests Single 12-lead ECGs evaluated by Investigator Vital signs assessed from time of first dose to end of study participation	2 3 4 5
To characterize the effect of evobrutinib on EE/NET PK	Plasma EE/NET: t _{max} t _{1/2} AUC _{0-t_{last}} CL/F VZ/F	6

ECG=electrocardiogram; EE/NET=ethinyl estradiol/ norethisterone; PK=pharmacokinetics; TEAE=treatment-emergent adverse event.

Overall Design: This will be a nonrandomized, open-label, single-sequence, multiple-dose Phase I study in a maximum of 20 healthy female participants.

Brief Summary:

The purpose of this study is to assess the effect of evobrutinib on the pharmacokinetics of a combined oral contraceptive in healthy female participants. Study details include:

Study Duration: up to 46 days

Treatment Duration: Days 4 to 17 (14 days treatment with evobrutinib); Days 1 and 15 (2 days treatment with COC)

[figure not shown]
Visit Frequency: Participants will be resident in the Clinical Research Unit from Day -1 to Day 18.

CCI

Study Intervention Groups and Duration: single-sequence study, up to 46 days

Involvement of Special Committee(s): No

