procedures met the protocol-specified criteria and were performed within the time frame defined in the Schedule of Assessments.

- Safety results that could unblind the study will not be reported to investigative sites or other blinded personnel until the study has been unblinded.

Note: This is not applicable in this study, since the study is open-label.

- No more than 100 mL of blood may be drawn in a 24-hour period, and no more than 300 mL of blood in a 4-week period.
- Where allowed by local law/regulations, samples collected during this clinical study may be transferred to a biobank and used for future research outside the clinical protocol when additional consent for this purpose is given. Transfer to the biobank will be documented and any testing of coded biobank samples will not be reported in the CSR.
- The long-term storage of samples after study completion for future research may be performed will all sample types collected in the study (e.g., PK, pharmacogenetics, biomarkers, or immunogenetic) if the participant consents to optional future medical research.

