8.3.7 Adverse Events of Special Interest

For this study, AESI(s) include only the following:

- Infections (serious, severe, and opportunistic, \geq Grade 3)

As per its mechanism of action, evobrutinib may impair B cell function which might lead to a decreased humoral immunity and consequently an increased risk of infection. Overall, in completed studies in participants the Medical Dictionary for Regulatory Activities SOC infection was one of the most reported SOCs (e.g., in the MS200527_0086 RMS study approximately 18% to 32% of participants treated with evobrutinib reported infection; a similar rate was reported in the placebo group in the 0 to 24 week period), the individual events were of low grade, mainly Grade 1, nonserious and did not lead to study intervention discontinuation. Treatment of infections must be prompt and done in accordance with local standard of care depending on considerations such as the nature and severity of the infection and participant's overall health status. Any Common Terminology Criteria for Adverse Events Grade ≥ 3 or SAEs of infection and opportunistic infection are considered as an AESI.

- Seizures

Seizures are more common in patients with MS than in the general population, occurring in 2% to 3% of MS patients (Poser 2003). Convulsions were observed in early studies of evobrutinib in dogs, however the plasma concentration of evobrutinib was approximately 140-fold greater than it is predicted for the dose used in this study. One participant with RMS with significant brain lesion load reported seizure of unclear clinical picture. The PK data for this participant did not exceed the expected values and was similar to other participants in the study. Anticonvulsant therapy was started, and the participant continued treatment with evobrutinib with no reoccurrence. The Investigator did not consider the event to be related to evobrutinib. No event of convolution/seizure was reported in other indications. Evobrutinib has been administered to approximately 800 patients with MS, rheumatoid arthritis and systemic lupus erythematosus. Moreover, an electroencephalogram study in healthy volunteers did not show an epileptogenic potential for evobrutinib. Any type of seizures/epilepsy of any grade or its consequences are classified as AESIs.

- Elevated lipase, elevated amylase, pancreatitis

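### Exclusion criterion 10 restricts a live vaccine given between Screening and admission less than a non-live one

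*Protocol*

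**What the plan says.** Criterion 10 in Protocol Section 5.2 holds two vaccine rules with different anchors.

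- **Live vaccines.** The excluded event is "Administration of live vaccines or live-attenuated virus vaccines within 3 months prior to Screening". The look-back ends at the Screening visit. Nothing is said about the time from Screening to admission or about the study itself.
- **Other vaccines.** Their use "is allowed until 4 weeks before admission to CRU, thereafter it is prohibited until the end of the study". This rule is anchored at admission and runs forward through the study.

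A note under the criterion asks that anyone with clinical symptoms be free of them for a week before admission.

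Criterion 5, in the same table, handles the same interval explicitly. It excludes "infections within 30 days prior to Screening and at any time between Screening and admission".

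The Schedule of Activities (Protocol Section 1.3) places Screening on Day -28 to Day -2 and repeats the eligibility check on Day -1. The Synopsis states: "Participants will be resident in the Clinical Research Unit from Day -1 to Day 18". Section 8.3.7 gives the reason for treating serious infection as an event of special interest: "evobrutinib may impair B cell function which might lead to a decreased humoral immunity and consequently an increased risk of infection".

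**The concern.** The criterion ranks live vaccines as the more restricted class, with a 3-month look-back against 4 weeks for the rest. Because the live-vaccine look-back stops at Screening and the other rule does not, the ranking reverses for a vaccine given between Screening and admission: the non-live vaccine is barred and the live one is not.

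Sections 5 and 8 prohibit waivers, so sites are expected to apply the criteria as written. Read literally, the text would let a participant start 14 days of evobrutinib soon after a live vaccine, in a study whose own safety section links the drug to reduced humoral immunity. What is at stake is participant safety and the interpretation of any infection that follows.

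**Working it through.** **Inputs**

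- Screening window: Day -28 to Day -2 (Protocol 1.3).
- Admission: Day -1 (Protocol 1.1).
- Day numbering: no Day 0 (SAP 9.2).
- First dose of any study intervention: Day 1. First evobrutinib dose: Day 4 (Protocol 6.1).
- General medicines ban: the longer of 2 weeks or 5 half-lives before first dose (Protocol 5.2 criterion 13, and 6.8.3).

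**Check of the day count.** Day -28 to Day 18 inclusive, with no Day 0, is 28 + 18 = 46 days. This reproduces the protocol's maximum of 46 days.

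**Step 1: Screening to admission.** The earliest Screening gives 28 - 1 = 27 elapsed days, and the latest gives 2 - 1 = 1 day.

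**Step 2: reach of the non-live rule.** Four weeks before Day -1 is Day -(1 + 28) = Day -29. That is one day before the earliest possible Screening, so a non-live vaccine is barred throughout the interval whatever the Screening date.

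**Step 3: reach of the live rule.** It covers none of the interval. With Screening on Day -28, the open days run from Day -27 to Day -2, which is 27 - 2 + 1 = 26 calendar days.

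**Step 4: if a vaccine counts as a prescribed medicine.** Two weeks before Day 1 is Day -14, so Day -14 onward is covered. This takes the 2-week limb, on the assumption that no half-life would be applied to a vaccine. The open days are then Day -27 to Day -15, which is 27 - 15 + 1 = 13 days.

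**Step 5: distance to evobrutinib.** From Day -d to Day 4 is d + 4 - 1 = d + 3 days.

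| Vaccine day | Days before first evobrutinib dose | Open on which reading |
|---|---|---|
| Day -27 | 27 + 3 = 30 | both |
| Day -15 | 15 + 3 = 18 | both |
| Day -2 | 2 + 3 = 5 | only if a vaccine is not a prescribed medicine |

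**Step 6: dependence on the Screening date.** For Screening on Day -s, the open days number s - 2 on the wider reading. On the narrower reading they number s - 15, or none when s is 15 or less. At s = 28 these give 26 and 13; at s = 15 they give 13 and 0.

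**Which reading applies.** Section 6.8 lists vaccines as a separate item from prescription and over-the-counter medicines when it says what to record. Criterion 13 and Section 6.8.3 do not name vaccines. The documents do not settle the question, so both figures are kept.

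**The case against.** The strongest reply is that the intent is plain. A criterion that gives live vaccines the longer look-back, and allows only other types up to 4 weeks before admission, would be taken by most investigators to bar live vaccines then too. There are also real backstops. Inclusion criterion 2 requires overt health. Criteria 1, 11 and 15 cover relevant disorders, investigator concern and ongoing findings. Examination, laboratory tests and eligibility are repeated on Day -1, and vaccines are recorded from consent, so the site would know of the event. This stands, and it is why the point is minor. It does not supply the missing rule. The general criteria and the note to criterion 10 turn on health, symptoms or opinion, not on the fact of vaccination. The Day -1 check re-applies the same text. Section 6.8.4 starts on Day -1 and points back to Section 5.2.

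A reader might infer that every look-back ending at Screening has the same defect. The documents do not support that:

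- A new shingles episode is a viral infection, and criterion 5 excludes it up to admission.
- The plasma and platelet clauses of criterion 27 give a start and no end, so they can be read as continuing.
- The Screening anchors for surgery ("any clinically relevant surgery within 3 months prior to Screening") and tropical travel contradict nothing else in the protocol.

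A reader might also set a blood donation against the Section 8 limit of "no more than 300 mL of blood in a 4-week period". That limit sits among the study procedures, and nothing in the documents counts earlier donations toward it.

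**Conclusion.** Criterion 10 is internally inconsistent. A live vaccine after Screening is less restricted than a non-live one for up to 26 calendar days, or up to 13 if vaccines fall under the general medicines ban. These are maxima at the earliest Screening date, and they assume that a vaccine given on the Screening day itself is caught at that visit. The gap shrinks as Screening moves closer to admission. The documents do not say how often participants will be screened early or vaccinated in the interval.

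Severity is minor. The primary comparison, Day 15 against Day 1 within participant, is not affected, and nothing in the documents ties vaccine timing to contraceptive exposure. It would also be too strong to conclude that investigator discretion under criterion 11 is the only remaining safeguard, given the others listed above.

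One secondary observation is optional. The whole-blood clause of criterion 27, "Donation or loss of more than 450 mL of blood in the 60 days prior to Screening", also ends at Screening and may leave the same interval open for losses above 450 mL.

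**What to change.** Reconcile the two sentences of criterion 10 so that the live-vaccine restriction does not lapse before the one already stated for other vaccines. The phrase in criterion 5 that extends its window from Screening to admission is an existing model. The length of any window is for the sponsor to decide. The sponsor should also say whether a vaccine counts as a medicine under criterion 13 and Section 6.8.3, because that alone moves the open interval from 26 to 13 days.

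Optionally, check the whole-blood clause of criterion 27 for the same gap.

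The cost is a wording change and one question at the Day -1 eligibility re-check that is already scheduled. The downside is an occasional candidate lost at admission.

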5.3 Lifestyle Considerations

5.3.1 Meals and Dietary Restrictions

Abstain from consumption of the following from 14 days before the start of study intervention until after the final dose: Seville oranges, grapefruit or grapefruit juice, pomelos, exotic citrus fruits, grapefruit hybrids, and juices from these fruits.

5.3.2 Caffeine, Alcohol, Tobacco, and Cannabinoid

- During each dosing period, participants will abstain from ingesting caffeine- or xanthine-containing products (e.g., coffee, tea, cola drinks, and chocolate) for 48 hours before the start of dosing until after collection of the final PK and/or pharmacodynamic sample.
- During each dosing period, participants will abstain from alcohol and cannabinoid-containing products for 24 hours before the start of dosing until after collection of the final PK and/or pharmacodynamic sample.

Note: In this study the consumption of alcohol is not allowed from 48 hours prior to first administration of study intervention (see Section 5.2) until after collection of the final PK sample.

- Use of tobacco products will not be allowed from at least 6 months preceding Screening until after the final follow-up visit.

5.3.3 Activity

Participants will abstain from strenuous exercise for 72 hours before each blood collection for clinical laboratory tests. Participants may participate in light recreational activities (e.g., watching television or reading).

5.4 Screen Failures

Individuals who do not meet the criteria for participation in this study (screen failure) may not be rescreened with the following exceptions:

- The participant successfully passed the screening procedures but subsequently could not start the study on schedule.
- Initial screening occurred too early to complete the required washout period after any prior therapy.
- The participant was not included due to transient reasons (e.g., an infection at the time of screening).
- Minor (not clinically relevant, as judged by the principal investigator) excursions of the inclusion/exclusion criteria may entitle the participant for rescreening.

Rescreening will be limited to 2 rescreenings per participant.

If an individual is to be rescreened, signature of a new ICF will be required.

